#### *10.1.1 Statistical power calculation for sample size (R33 phase):*

While we have demonstrated resolution of extremely severe OSA in our initial patients with hypotonia, the sample size calculation for the current trial is based on conservative assumptions. We defined a treatment response as meeting both a 50% reduction in AHI (e.g., 12.8 to 6.4) and post-treatment AHI<15 at Week 8. We considered this as the clinically meaningful improvement and designed the study to detect a difference in the proportion of children meeting clinically

meaningful improvement in OSA of 60% in the ssNPA device group vs. 18% in the SoC group. To detect a between-group difference of 60% vs. 18%, we will enroll 20 children per arm, for a total of 40 children, which will provide 80% power using a two-sided 0.05 level test. The study power will differ by the various assumptions. In particular, if the treatment response occurs in 15% or 20% of the ScC group enrollees, the proposed sample size will provide 75% and 86% power to detect the respective between-group differences in treatment response. We note that if a patient requires a tracheostomy within the 8 weeks of randomization, the patient will be considered not to have a treatment response. We expect further adjusting the primary analysis for baseline values of AHI will likely increase the power to detect the meaningful difference. For continuous outcomes such as PSQ or PedsQL, the proposed sample size is expected to give 80% power to detect an effect size of 0.89 SD or larger. We conservatively assume up to 20% dropout from the study where neither a tracheostomy nor a PSG is done, and to ensure that a total of 40 children have complete outcome data, we will enroll 50 children.

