In secondary analyses, we will use linear mixed models and fit longitudinally assessed outcomes data at baseline, Weeks 8 and 16 to assess the long-term effects of ssNPA. For binary treatment response, the outcomes assessed at Week 8 and 16 will be modeled using a generalized mixed model with logit link. The model will include participants as random intercepts and will include the ssNPA arm indicator, categorical time indicators for Weeks 8 and 16, and interactions of Week 8 by arm and Week 16 by arm. A significant interaction of Week 8 by ssNPA arm will provide evidence for ssNPA effect, and showing no difference in the coefficients between the two interaction terms of Week 8 by ssNPA arm and Week 16 by ssNPA arm will indicate NPA effect to remain long-term over the 4-month period. Prior to the longitudinal data modeling, we will graph cross-sectional means of outcome measures (e.g., percentage with treatment response) with SoC group stratified further to those that opted to receive ssNPA at Week 8 vs. not to visualize if their Weeks 8 and 16 data should be treated as a separate group or can be treated as additional data to ssNPA arm data. The data and model will allow us to explore for sub-hypotheses if the number of SoC group patients receiving ssNPA at Week 8 is substantial. We note, however, that the Week 16 outcomes of SoC group patients will be interpreted carefully as they reflect outcomes in participants who opt to use or not use ssNPA after having been exposed to the standard care under a research setting for an 8-week period.

Of critical importance will be subgroup of patients who have OSA severity with AHI>30. These Patients with HUAO and extremely severe OSA are likely to fail surgical interventions other than tracheostomy and as such will be considered “warranting tracheostomy”. Given the proposed sample size and the known prevalence of about 20% of hypotonic patients with severe apnea, we expect a total of about 8-10 patients “warranting tracheostomy”. We will report, by each arm, the number (%) receiving tracheostomy in all study enrollees and in those with baseline AHI>30 by Week 8. We will also report the number (%) receiving tracheostomy in those randomized to ssNPA arm by Week 16. These data will be used for future power calculations to determine sample size requirements for larger trials focused on the utility of the ssNPA in tracheostomy avoidance.

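### Secondary logit model for binary response: the Week 8 by arm coefficient that is to carry the evidence for an ssNPA effect cannot be estimated as specified

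*Combined protocol and SAP*

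**What the plan says.** The secondary analyses in Section 10.2.2 begin with linear mixed models that "fit longitudinally assessed outcomes data at baseline, Weeks 8 and 16". The text then turns to the responder outcome: "For binary treatment response, the outcomes assessed at Week 8 and 16 will be modeled using a generalized mixed model with logit link". The next sentence lists the terms: "The model will include participants as random intercepts and will include the ssNPA arm indicator, categorical time indicators for Weeks 8 and 16". The same sentence adds an arm interaction for each of the two weeks.

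Two readings of the coefficients are fixed in advance. The first is: "A significant interaction of Week 8 by ssNPA arm will provide evidence for ssNPA effect". The second is that "showing no difference in the coefficients between the two interaction terms" will indicate that the effect lasts over the four months.

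Section 10.1.1 defines the outcome: "We defined a treatment response as meeting both a 50% reduction in AHI (e.g., 12.8 to 6.4) and post-treatment AHI<15 at Week 8". Response is therefore judged against the child's own baseline AHI.

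**The concern.** An arm indicator, one indicator per follow-up week and one interaction per follow-up week make a sound model when a third time level, baseline, serves as the reference. Each interaction then measures how far the arms have moved apart since baseline. The continuous outcomes have that level. The binary response does not, because at baseline it is either undefined or a non-response for every child.

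Without a reference level the listed terms are redundant, and the coefficient in the first reading has no unique value. Whoever runs the model must remove or constrain something, and that choice decides what the printed Week 8 by arm line means. At stake is a prespecified inferential statement about the responder endpoint, whose meaning would be settled only at the time of analysis.

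**Working it through.** **Inputs.** Two arms, and response at Weeks 8 and 16 only (Section 10.2.2). Planned Week 8 response of 60% on ssNPA and 18% on SoC, 20 per arm, two-sided 0.05 (Section 10.1.1). SoC children are offered the device at Week 8 (Sections 9.4 and 9.4.2). The documents give no Week 16 response rates, so those used below are assumptions.

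**The plan's own figure.** No power is stated for this secondary model. The nearest figure is the 80% for the primary test. With pooled variance under the null, mean rate 0.39:

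z = [0.42 × √20 − 1.96 × √(2 × 0.39 × 0.61)] / √(0.60 × 0.40 + 0.18 × 0.82) = (1.878 − 1.352) / 0.623 = 0.845, so power = 80.1%.

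The plan's figure is reproduced, and the point below does not touch it.

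**Design matrix for the binary outcome** (A = ssNPA arm):

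| Cell | Intercept | A | W8 | W16 | A×W8 | A×W16 |
|---|---|---|---|---|---|---|
| SoC, Week 8 | 1 | 0 | 1 | 0 | 0 | 0 |
| SoC, Week 16 | 1 | 0 | 0 | 1 | 0 | 0 |
| ssNPA, Week 8 | 1 | 1 | 1 | 0 | 1 | 0 |
| ssNPA, Week 16 | 1 | 1 | 0 | 1 | 0 | 1 |

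There are two exact dependencies: Intercept = W8 + W16, and A = A×W8 + A×W16. Rank = 6 − 2 = 4. Without an intercept, which the text does not list, only the second dependency remains, and rank = 5 − 1 = 4. The participant random intercept does not alter the fixed-effect columns.

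**Which terms are estimable.** Add any constant c to the A coefficient and subtract c from both interaction coefficients. All four fitted values are unchanged, so neither interaction has a unique value, with or without an intercept. In the difference A×W8 − A×W16 the constant c cancels, so that difference is estimable.

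**With a baseline level.** Adding the two baseline rows, (1,0,0,0,0,0) and (1,1,0,0,0,0), brings the six columns to rank 6, and every term is estimable. That is the position of the continuous outcomes. It does not help the binary outcome: if response is coded 0 for everyone at baseline, the baseline cells are completely separated and the coefficients diverge.

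**What one likely reduction would give.** If Week 16 and Week 16 by arm are dropped, the cells give

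A = logOR(Week 16) and A×W8 = logOR(Week 8) − logOR(Week 16).

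On the cell-rate scale, ignoring the random intercept, logit(0.60) = 0.405 and logit(0.18) = −1.516, so logOR(Week 8) = 1.92. With ssNPA assumed to stay at 60% at Week 16:

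| SoC response at Week 16 (assumed) | logOR(Week 16) | Printed Week 8 by arm term |
|---|---|---|
| 18% | 1.92 | 0.00 |
| 39% | 0.85 | 1.07 |
| 60% | 0.00 | 1.92 |

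The Week 8 effect is 1.92 in every row. The printed term tracks the SoC arm's change after Week 8. It is also the quantity that the second reading compares with zero, so under this reduction one contrast would have to be significant to show an effect and null to show that the effect lasts.

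**The case against.** The strongest reply is that this is one secondary model. Section 10.2.2 makes the two-sample proportion test at Week 8 the primary analysis of the same endpoint, says that the longitudinal models are there to assess long-term effects, and cautions about interpreting Week 16 results in the SoC group. All of that stands. A reader might infer that the trial could miss a real device effect. The documents do not support this, because the Week 8 conclusion rests on the primary test.

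A second reply is that the part of the rule that serves the long-term question survives. This also stands: the difference between the two interactions does not depend on which columns are removed.

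A third is that the listed terms may be a general longitudinal specification carried over from the continuous outcomes. That is plausible, but the list directly follows the sentence on binary response. If it was not meant for that outcome, the binary model has no stated terms and the text still needs correcting.

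A reader might also infer that software will silently produce a wrong answer. The documents name no software, coding or reference level. With Week 8 as the reference there would be no Week 8 by arm line, and the analyst would notice. If the arm main effect and the intercept were removed instead, the term would mean what the plan intends. The reduction shown above is one possibility.

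Simulated rejection rates add little. With 20 per arm, an assumed within-child latent correlation of 0.6 and marginal logit fits, the reduced term is significant in about 4–5%, 27–31% and 69–71% of trials for SoC Week 16 rates of 18%, 39% and 60%. The first is simply the size of the test. Varying the correlation from 0 to 0.9 moves the other two to roughly 16–42% and 57–88%. None of these is the planned random-intercept fit.

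**Conclusion.** The point holds for the binary logit model as written. Four cells cannot support five or six fixed effects, and the Week 8 by arm coefficient named in the first reading is not estimable. This follows from the text and needs no assumption. The illustrative values of 0, 1.07 and 1.92 do rest on assumptions: that Week 16 and Week 16 by arm are the terms removed, that ssNPA stays at 60% at Week 16, and the SoC Week 16 rates shown. They indicate that the remaining term would not measure the Week 8 effect.

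The persistence comparison, the continuous-outcome models with baseline data, and the primary test with its power are not affected. This is a should-fix item for a secondary analysis.

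**What to change.** For binary response only, replace the list of terms with one full-rank form:

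- **Week 8 as reference:** intercept, arm, Week 16 and Week 16 by arm. The arm coefficient is the Week 8 ssNPA effect, and Week 16 by arm is the change in that effect.
- **Cell form:** Week 8, Week 16, Week 8 by arm and Week 16 by arm, with no intercept and no arm main effect. Week 8 by arm is the Week 8 log odds ratio, and the difference between the two interactions is the change. This stays closest to the existing wording.

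Then reword the decision rule to name the matching coefficient for the Week 8 effect, and keep the persistence comparison. State that the present list of terms applies to the continuous outcomes with baseline data. The random-intercept logit model can stay; a marginal model would be a matter of preference.

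The cost is a few sentences in the SAP, best settled before outcome data are analysed. There is no cost in data, patients or timeline.

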### 9.4 R33 Phase – Randomization

After the R61 phase is successfully completed, for the R33 phase we will recruit 40 children with HUAO meeting the inclusion criteria of severe OSA (AHI>10 or >5 with hypoxemia) with the additional requirement that all subjects require the presence of at least one symptom of OSA (such as snoring 3 or more nights per week, daytime sleepiness, or hyperactive/inattentive behaviors). These latter symptoms will identify children at the highest risk for OSA and will minimize false positive from the baseline PSG. The exclusion criteria are the same as those delineated in the R61 phase clinical study.

Recruitment will occur from all clinics as well as community sources. In order to ensure that sufficient children complete the protocol and we have enough data from 40 subjects for our data analysis, we may recruit up to a total of 50 subjects to include for those children who may drop out before the end of 8 weeks study. All children will undergo a baseline PSG to determine eligibility and establish baseline data. All families will complete a questionnaire battery at the time of baseline PSG to acquire baseline measures. Eligible patients will be randomized 1:1 to receive (1) immediate therapy with the ssNPA device or (2) standard of care (SoC). The study will be designed as a randomized wait-list controlled clinical trial such that all children stand to benefit. Randomization will be stratified by baseline AHI scores (AHI>30 vs.  $\leq 30$ ).

At 8 weeks the ssNPA group will be able to continue the ssNPA for an additional 8 weeks while the SoC group will be offered the ssNPA for 8 weeks. At the end of the 8 week period, all children will undergo an in-laboratory PSG and repeat the questionnaire battery.

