### *10.2.2 R33 Phase Statistical analysis:*

We will summarize subject characteristics by study arm. We will also summarize outcomes data at each assessment time and changes from baseline in outcome measures at each follow-up time by arm using appropriate summary measures including means, standard deviations, and proportions. If the data are highly skewed such as increasing variability with increasing mean, we will consider log-transformation. Primary outcomes will be treatment response at Week 8, defined as a clinically meaningful improvement in AHI of 50% reduction and AHI<15, and primary analytic cohort will be intent-to-treat. For the comparison of treatment response, receiving tracheostomy prior to Week 8 will be considered a treatment response failure. Although post treatment data are collected at Weeks 8 and 16, primary comparative analysis will be done using Week 8 data as the SoC group patients initiating the ssNPA at Week 8 will have self-selected to use the device and are not parallel to those initially randomized to the ssNPA. The between-arm difference in treatment response will be compared using a two-sample proportion test. Secondary outcomes will include various patient and caregiver outcome measures including AHI, PSQ, PedsQL and OSA-18. Improvement in each of these continuous measures will be compared between arms using mixed models with data at both baseline and Week 8 as the dependent variables, participants as random intercepts and an indicator for the ssNPA arm, an indicator for Week 8, and an interaction of Week 8 by ssNPA arm as the primary predictors. The parameter of the Week 8 by ssNPA arm interaction term will estimate the ssNPA effect. We will separately

report dropouts by arm and collect data on reasons for dropping out of the study. If dropout rate is more than 10%, for each outcome variable, we will perform an alternate parallel analysis where we will weigh the between-arm response comparisons inversely by the propensity of dropping out, with the propensities estimated separately from a logistic regression predicting dropout using baseline patient characteristics (e.g., age, sex, baseline AHI, treatment arm).

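### The Week 16 rule takes an undefined absence of difference between two arm-by-time coefficients as showing a lasting effect, and no handling of SoC children who take up the device makes it valid

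*Combined protocol and SAP*

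**What the plan says.** Section 10.2.2 assigns the long-term question to mixed models. For binary response these use Weeks 8 and 16, with an arm indicator, "categorical time indicators for Weeks 8 and 16, and interactions of Week 8 by arm and Week 16 by arm". The reading rule turns on "showing no difference in the coefficients between the two interaction terms of Week 8 by ssNPA arm and Week 16 by ssNPA arm". Such a result, according to the plan, "will indicate NPA effect to remain long-term over the 4-month period".

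Section 9.4 has the ssNPA arm able to continue for a further 8 weeks "while the SoC group will be offered the ssNPA for 8 weeks". Section 9.4.2 makes that offer voluntary. No uptake figure is given.

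The plan sees part of the difficulty. Section 10.2.2 keeps the primary comparison at Week 8 because late starters "have self-selected to use the device and are not parallel to those initially randomized to the ssNPA". Before modelling, outcomes are to be graphed with SoC divided by uptake, to see whether the opt-ins' data "should be treated as a separate group or can be treated as additional data to ssNPA arm data". The section asks for caution over SoC Week 16 results, and it summarises outcomes and "changes from baseline in outcome measures at each follow-up time by arm". It also says that "receiving tracheostomy prior to Week 8 will be considered a treatment response failure", but gives no matching rule for Week 16.

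Durability is not among the R33 objectives in sections 4.3 and 4.4.

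**The concern.** There are two separate faults, and they pull in opposite directions.

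First, the two coefficients need not estimate the same thing. At Week 8 the arms differ by device against SoC. At Week 16, with arms as randomised, they differ by early against delayed offer of the device. A change between the two can come from waning in the ssNPA arm, from uptake in the SoC arm, or from both.

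Second, failing to find a difference is not evidence of sameness unless a tolerable loss has been fixed and the data exclude it. The trial is sized for a 42-point contrast at one visit. A change in that contrast between visits is estimated much less precisely.

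At stake is the trial's statement on whether benefit lasts four months. A real loss could be reported as lasting benefit, or a lasting benefit could go uncredited.

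**Working it through.** **Inputs from the plan (section 10.1.1):** 20 children per arm; response 60% on ssNPA and 18% on SoC at Week 8; two-sided 0.05.

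**Assumptions, because the plan gives no figure:** SoC uptake u; response r among late starters; within-child correlation 0.3-0.9 on a latent normal scale; the rule read as p>0.05.

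**1. The plan's own figure.** Pooled two-proportion test with mean proportion 0.39: z = (0.42·√20 − 1.96·√(2·0.39·0.61)) / √(0.6·0.4 + 0.18·0.82) = (1.878 − 1.352)/0.623 = 0.845. Power is 80.1%, so the stated 80% reproduces. No power or precision is stated for the Week 8 against Week 16 contrast.

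**2. Opt-ins analysed as randomised.** SoC response at Week 16 is u·r + (1 − u)·0.18. Let the ssNPA effect last fully, with 60% at both visits:

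| Uptake | r | SoC at Week 16 | Arm difference at Week 16 (Week 8: 42 points) |
|---|---|---|---|
| 50% | 60% | 39% | 21 points |
| 100% | 60% | 60% | 0 points |
| 50% | 40% | 29% | 31 points |
| 100% | 40% | 40% | 20 points |

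Full uptake at r = 60% with a fully lasting effect gives a contrast of 0 − 42 = −42 points. Complete loss in the ssNPA arm (60% to 18%) with no uptake also gives 0 − 42 = −42. The contrast cannot tell these apart.

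In simulations of the planned logit random-intercept model at 50% uptake, a fully lasting effect gave p<0.05 in about 24-40% of trials with r = 60%, and about 14-20% with r = 40%. With no uptake the figure is about 6%.

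**3. Opt-ins split off.** This removes uptake from the comparator but leaves only decliners. With 10 decliners, a true fall from 60% to 40% in the ssNPA arm is missed (p>0.05) in about 80-88% of trials under the same model.

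**4. Opt-ins pooled with ssNPA.** The graph that decides this has no criterion. Pooling would merge a randomised arm with children whom the same section describes as self-selected, and decliners would again be the comparator. No error rate was computed for this option; the objection to it is structural.

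**5. Real waning, no uptake, 20 per arm.** For a true fall from 60% to 40%, the planned model misses it in about 71-84% of trials. The figure depends on the test: about 57-77% for a Wald test on the risk difference, and 80-88% for a Wald test on the marginal log-odds. As a hand check on the risk-difference scale, the simulated standard error is 0.179 at correlation 0.3, so power is about Φ(0.20/0.179 − 1.96) = Φ(−0.84) = 0.20 and about 80% are missed (78% simulated).

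**6. Precision of the within-arm alternative.** At a stable 60%, the 95% half-width for the Week 16 minus Week 8 change is 1.96·√(d/20), where d is the proportion of children whose response differs between visits. With d = 0.388 (correlation 0.3) it is 0.273; with d = 0.139 (correlation 0.9) it is 0.163.

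**The case against.** The best defence is that the plan does not commit to leaving opt-ins in the SoC comparator. It names two options, a separate group or pooling with ssNPA, and the uptake figures in step 2 apply to neither. That stands: those figures are conditional on an as-randomised analysis, which the arm indicator permits but the text does not confirm. It does not rescue the rule, because steps 3 and 4 show that each named option fails for a different reason.

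It is also fair that no test is named, so the missed-waning figures depend on reading the rule as p>0.05, and that they cover binary response only. The absence of a margin or interval criterion is certain; the percentages are conditional.

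The call for caution and the by-arm summaries make an unnoticed error less likely. Neither changes the rule, and neither provides an interval for the Week 8 to Week 16 change.

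A narrower repair would keep the contrast, add a margin and fix the opt-in handling. With arms as randomised, a margin would still be applied to a mixture of waning and uptake.

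A reader might infer that high uptake leads the plan to declare a false loss of effect. The text does not support that: it does not say what a difference would mean, so a lasting effect would go uncredited rather than be contradicted.

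**Conclusion.** The point holds for a secondary analysis and should be fixed. Section 10.2.2 states an operative rule that cannot support a durability conclusion under any of the three ways of handling SoC opt-ins, and it sets no margin.

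The size of the problem rests on assumed uptake, late-starter response and within-child correlation. As randomised, a fully lasting effect can move the arm difference anywhere from 42 points down to 0. Under the p>0.05 reading with no uptake, a 20-point fall in response would be missed in roughly 70-85% of trials under the planned model, and in a majority under each test tried.

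A reader might go further and infer that the trial's efficacy result is compromised. It is not: the primary test uses Week 8 data, before SoC children are offered the device. Nor is a false durability claim inevitable. It requires real waning, low uptake or opt-ins split off, and a significance-based reading of the rule.

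**What to change.** Delete the rule based on the difference of coefficients and substitute wording such as:

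> Durability will be estimated as the Week 16 minus Week 8 change in treatment response, AHI, PSQ, PedsQL and OSA-18 in all children randomised to ssNPA, whether or not they keep using the device, each with a 95% CI, and reported as an estimate. No yes/no claim will be made unless a largest acceptable loss is fixed before Week 16 outcomes are summarised by arm and the CI excludes it. Tracheostomy at any time before Week 16, including before Week 8, counts as non-response at Week 16. One stated missing-data approach, including the dropout weighting in section 10.2.2, applies to missing Week 8 and Week 16 data. The Week 16 between-arm contrast compares immediate with delayed offer of ssNPA, analysed as randomised. SoC results by opt-in are descriptive and are not pooled with the ssNPA arm.

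This changes SAP wording only. Section 9.4.1 already schedules the Week 16 PSG and questionnaires for the ssNPA arm.

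There are two costs. The within-arm change has no concurrent control, so device durability cannot be separated from natural change or night-to-night PSG variation. The interval is also wide, about ±16 to ±27 points with 20 children. As an illustration, with a truly stable 60% and an assumed 20-point margin, the chance of excluding that loss is Φ(0.20/√(d/20) − 1.96): about 30% at d = 0.388 and 67% at d = 0.139. The result will mainly be an estimate and should be presented as one.

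### A look at outcome graphs, with no stated criterion, may decide whether self-selected SoC children are added to the randomised ssNPA arm in the secondary longitudinal analyses

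*Combined protocol and SAP*

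**What the plan says.** All of this is in the combined protocol and SAP, Section 10.2.2, unless another section is named.

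- **Primary analysis.** The "primary comparative analysis will be done using Week 8 data", and the "primary analytic cohort will be intent-to-treat". The reason given for stopping at Week 8 is that SoC children who then start the device "will have self-selected to use the device and are not parallel to those initially randomized to the ssNPA".
- **Main secondary comparison.** Continuous outcomes are compared between arms by mixed models that use baseline and Week 8 only.
- **Longitudinal analyses.** Further models add Week 16. They contain randomised arm, categorical week indicators and arm-by-week interactions. If the Week 8 and Week 16 interactions do not differ, the plan will conclude that the effect lasts.
- **Grouping step.** "Prior to the longitudinal data modeling, we will graph cross-sectional means of outcome measures" ("e.g., percentage with treatment response"), with the SoC arm split into children who took up ssNPA at Week 8 and those who did not. The purpose is to see whether their data "should be treated as a separate group or can be treated as additional data to ssNPA arm data". No test, margin or other criterion follows.
- **Cautions.** Sub-hypotheses may be explored "if the number of SoC group patients receiving ssNPA at Week 8 is substantial", with no threshold for that number. The plan adds that "the Week 16 outcomes of SoC group patients will be interpreted carefully".
- **Uptake is a choice.** Under Section 9.4.2, SoC families may accept or decline the device at Week 8. Both arms have sleep studies at Weeks 8 and 16.

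**The concern.** The make-up of the ssNPA group in the longitudinal analysis may be settled by inspecting the outcome that the analysis then estimates. The children concerned chose the device after 8 weeks of standard care, and the plan itself gives this as a reason not to compare them directly with the randomised arm.

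The long-term estimate is at stake. If the records were merged, it would combine randomised and self-selected children with different times on the device, and its composition would depend on the data. A reader could not tell how far the result reflects the device and how far it reflects who opted in.

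The criterion for durability has a related weakness. If opt-in children stay in the SoC arm, they are on the device at Week 16, so the between-arm contrast shrinks even when the device works as well as before.

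**Working it through.** **Inputs from the plan.** Section 10.1.1: 20 children per arm, response 60% (ssNPA) and 18% (SoC), 80% power, two-sided 0.05. Sections 9.4.1 and 9.4.2: when the device starts and when sleep studies are done.

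**Assumptions, because the plan gives no figure.** The number of SoC children who opt in (10, 16 or 20 of 20; the last needs every child to opt in and none to be lost), their response rate, and the gap that would be read off a graph as similar.

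**1. The plan's own figure.** Pooled-variance test, mean rate (0.60 + 0.18)/2 = 0.39:
- standard error under no difference: √(2 × 0.39 × 0.61/20) = 0.154
- standard error under the alternative: √((0.60 × 0.40 + 0.18 × 0.82)/20) = 0.139
- (0.42 − 1.96 × 0.154)/0.139 ≈ 0.845, which gives power 80.1%. The stated 80% reproduces.

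**2. What a graph could show.** With both groups at 60%, the 95% half-width for the difference between 20 randomised ssNPA children and m opt-ins is 1.96 × √(0.6 × 0.4 × (1/20 + 1/m)):
- m = 10: 0.37
- m = 16: 0.32
- m = 20: 0.30

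**3. What a visual rule could do.** Suppose self-selection raises the opt-in rate to 75% while the randomised arm is at 60%. The formula of step 1, with unequal group sizes, gives 11%, 15% or 17% power to detect this for m = 10, 16 or 20. Suppose also that the graph is read as similar when the observed rates lie within t of each other. Summing the binomial probabilities of all outcome pairs within t:
- t = 10 points: pooling in 37%, 34% or 40% of trials
- t = 20 points: pooling in 64%, 63% or 69% of trials

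With m = 16 the pooled rate is (20 × 0.60 + 16 × 0.75)/36 = 24/36 ≈ 67%, against a true 60% in the randomised arm. Restricting to trials in which pooling occurs also gives about 67%. If both true rates are 60%, the same readings would still refuse to pool in about 15% to 52% of trials.

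**4. Time on device at each record.**

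| Record | Randomised ssNPA | SoC opt-in |
|---|---|---|
| Week 8 | about 8 weeks | none yet |
| Week 16 | about 16 weeks | about 8 weeks |

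The grouping sentence covers both weeks' data, so it is unclear what an opt-in child's Week 8 record would add to the ssNPA arm.

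**5. The Week 16 contrast by randomised arm.** Assume that the ssNPA arm stays at 60%, opt-ins reach 60% and decliners stay at 18%. With k of 20 opting in, SoC response at Week 16 is (0.60k + 0.18(20 − k))/20:
- k = 10: 7.8/20 = 39%, difference 21 points
- k = 16: 10.32/20 = 52%, difference 8 points
- k = 20: 12/20 = 60%, difference 0 points

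At Week 8 the difference is 60 − 18 = 42 points. The device effect is fully maintained in every row, yet the contrast falls. The planned model for response works in log-odds, but the direction is the same.

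**The case against.** The strongest reply is that this is an under-specified exploratory step, and that its reach is narrow. Much of that stands.

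- **Primary result.** A reader might infer that the trial's main conclusion is exposed. It is not: neither the Week 8 intent-to-treat comparison nor the baseline-to-Week-8 models can be changed by the grouping choice.
- **Direction.** A reader might infer that the plan favours pooling when opt-in results look good, or that it contains a rule to pool whenever they look similar. The text states neither. On a similarity reading, opt-ins doing clearly better than the randomised arm would be kept apart. The text supports only that the choice depends on outcomes.
- **Contradiction.** The not-parallel statement explains why the primary comparison stops at Week 8, and the later text repeats a caution. This is a tension between two steps, and strictly not a contradiction. Careful interpretation, however, does not fix which model is fitted.
- **Blinding.** Section 11.5.2 confines aggregate outcomes to unblinded statisticians. That lessens worry about motive, but whoever draws the graphs still sees outcomes by group before the model is settled.
- **Mislabelled exposure.** No pooled model is written down, so it cannot be said that the plan would mislabel time on device. It states no realignment for these models, although it counts adherence from device initiation in both groups.
- **Meaning of the intervals.** They show how little a graph of two small groups can establish. They do not measure bias in a planned estimate.

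**Conclusion.** The point holds for the secondary longitudinal analyses only. There, a graph of the outcomes, with no criterion, is the only stated basis for keeping opt-in SoC children apart or adding them to the ssNPA arm data. With 20 randomised ssNPA children and an assumed 10 to 20 opt-ins, all at 60% response, the difference is uncertain by about ±37 to ±30 points, so similarity cannot be read from the graph. If opt-ins truly responded at 75%, merging 16 of them would move a 60% rate to about 67%. That shift is an illustration under assumed rates and not a prediction.

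Fitting the longitudinal model by randomised arm is already what the plan specifies, and it does not rescue the durability conclusion. Under the assumptions of step 5, crossover alone shrinks a 42-point contrast to about 21, 8 or 0 points. A change in the interaction therefore need not mean a lost effect, and equality of the two terms is not a sound test of persistence.

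**What to change.** In Section 10.2.2:

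1. State in advance that SoC children who opt for ssNPA at Week 8 are not merged with the randomised ssNPA arm, whatever the graphs show. The graphs remain as description.
2. Report these children's Week 8 to Week 16 change descriptively, with Week 8 as their pre-device baseline.
3. Base the durability conclusion on the Week 8 to Week 16 change within the randomised ssNPA arm, in place of equality of the two arm-by-week interactions.
4. Label any pooled analysis exploratory, align it on time since device start, and fix its rule before outcomes are seen.

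The cost is a few sentences; no sample size, visit or procedure changes. There are two downsides: one exploratory estimate has fewer records, and the durability estimate is a within-arm change without the protection of a randomised comparison. The report should say so.
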